9 TIMING OF STUDY PROCEDURES

Study subjects will receive study drug (FT218 or placebo) as outpatients. The study is divided into 4 sequential periods with a total of 9 required study visits. One in Period 1, one in Period 2, six in Period 3 (the double-blind period) concluding with a single follow-up visit in Period 4.

Where additional study visits are clinically required an unscheduled visit will be performed. A separate unscheduled eCRF visit module will be completed to record these visits. A set minimum of procedures to capture subject safety and progress will be done at the unscheduled visit, requirements for additional procedures will be determined by the PI/designee.

For early withdrawal, the EOS/Withdrawal eCRF module will be completed. In addition the EOS/Withdrawal eCRF page must be completed detailing the reason for subject withdrawal. The reason for withdrawal must also be recorded in the source documents.

Subjects will provide written informed consent as appropriate and according to local laws and regulations, before any study-related procedures are performed.

9.1 Pre-treatment – Periods 1 and 2

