9.3.1 Period 4: Visit 9 (Week 15, Day 1) Follow-up

A safety follow-up visit will take place at Week 15 Day 1 (+4/-0) when subjects have been off study drug for ≥ 1 week. Study procedures include:

- Review and record all concomitant medication
- Safety assessment: To include assessment for residual effects of study drug and all AE review.
 - All AEs including residual effects of study drug to be reported as per study protocol requirements. The outcome of any AEs with a date of onset during the double-blind period should be reevaluated and any new AEs should be recorded. All SAEs and nonserious AEs assessed by the PI as related to the study drug should be followed to resolution or until the PI assesses them to be chronic or stable
 - In the event that a study subject is unable to return to clinic for the follow-up visit, telephone contact with the study subject to assess for AEs and or residual effects of study drug and concomitant medications is expected.
- Perform physical examination if determined clinically indicated by the PI
- Collect weight
- Collect vital signs (systolic and diastolic BP and heart rate) if clinically indicated
- Collect samples for hematology or biochemistry if clinically indicated, and perform urine pregnancy test (female subjects)

- Discuss off-study narcolepsy therapeutic pathway with study subject

9.4 **Unscheduled Visits**

Where additional study visits are clinically required an unscheduled visit will be performed. Where an unscheduled visit leads to the subject's withdrawal, the procedures to be performed are those planned for the EOS visit as detailed in [Section 9.2.6](#).

Study procedures include:

- Compliance with drug washout requirements
- Confirmation of continued eligibility
- Assess study restrictions compliance: (i) abstinence from alcohol, (ii) smoking restrictions, and (iii) all other study restrictions
- Assess drug abuse and dependence. Clinical judgement to be exercised in determining need for performing urine drug screen for benzodiazepines, cannabis, cocaine, opiates and barbiturates
- Assess compliance with drug handling, management and safety requirements.
 - Confirm subject is adhering to requirement to eat at least 2 hours before taking study drug
 - Subject re-education on study drug safety and handling and study-related procedures if deemed necessary by site PI
- Review and record of concomitant medication
 - Assess for adherence to prohibited medication requirements
- Document any AEs

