If the investigator determines that the causality is unknown, the PI must then assign a causality of "Possibly" for the purposes of reporting. The causality must be clearly documented in the subject's medical notes and eCRF and report in accordance with the SAE reporting requirements if applicable.

Action Taken

The investigator will describe the action taken in the appropriate section of the eCRF, as follows:

- None
- Study drug stopped
- Study drug temporarily interrupted
- Concomitant medication
- Other, specify.

Adverse Event Outcome

The investigator will assess the outcome of the AE or SAE as follows:

- Fatal (the subject has died)
- Resolved (the AE or SAE has ended)
- Ongoing (the AE has not ended)*
- Unknown (lost to follow-up after repeated unsuccessful attempts to contact the subject)

* An AE outcome can only be categorized as ongoing if the AE is:

- Ongoing at the end of the reporting period: improved, stable or worsening
- Ongoing: improved, stable, or worsening, and referred to the subject's physician or a specialist.

Follow-up of Adverse Events

All investigators should follow up subjects with AEs until the event is resolved or until, in the opinion of the investigator, the event is stabilized or determined to be chronic. Details of AE resolution must be documented in the eCRF.

Subjects should be followed for 7 days after receiving the last dose of study drug, and any AEs that occur during this time should be reported according to the procedures outlined above.

Documentation and Reporting of Adverse Events

Attention will be paid to the occurrence of AEs at all stages of the clinical study starting from signing of the informed consent to the follow-up visit which takes place 1 week after study completion or 1 week after premature withdrawal. Baseline events (i.e. medical history events that are ongoing) captured at the first study visit will only be recorded as AEs if during the screening and assessment period or double-blind period there is deterioration.

Information regarding all AEs, including SAEs, will be collected at each visit. All AE/SAEs that are encountered during the protocol specified AE/SAE reporting period will be followed to their resolutions, until the investigator assesses them as stable, or the subject is lost to follow-up.

Adverse events will be identified as treatment-emergent (TEAE) if the event occurs or increases in severity after the first dose of study drug is taken.

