10.1.2.4 Physical Examination

A complete physical examination including weight and evaluation of main body systems/regions, including: skin and mucous, ears/nose/throat, pulmonary, cardiac, GI, and neurological systems.

In case of abnormality, a comment will be recorded in the eCRF and subjects medical notes. Any deterioration in condition will be reported as an AE.

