2.3 SCHEDULE OF EVENTS

The clinical trial design is comprised of four periods: screening, wash-out/baseline (which includes randomization), double-blind-treatment and follow-up. These are shown in Table 1. After randomization, the doses of the FT218 arm begins at 4.5 g where it remains for one week (Period 3a), then it is titrated to 6 g where it remains for two weeks (Period 3a), then to 7.5 g where it remains for five weeks (Period 3b (i) and 3b (ii)) and finally to 9 g for the final 5 weeks (Period 3c(i) and 3c(ii)).

[REDACTED]

Table 1. Schedule of Events				
Period	Week(s)	Phase of Study		Evaluations
1	Week -3 to Week 0	Week -3 Screening Visit Week -3 Day 1 Commence Sleep and Symptom Diary Week -1 D7 Overnight PSG and next day 4 Nap MWT		Full screening and enrolment evaluation Full Baseline Evaluation (D7 W-1 – PSG; D1 W0 Next day MWT)
2	Week 0***	Week 0 + Max 2 days Central Scoring Lab Results Week 0 D2 or D3 Randomization		
		FT218 Arm	Placebo Arm	
3a	Weeks 1-3	Week 1: 4.5g Week 2-3: 6.g	Placebo	Full Efficacy Assessment* Visit 4 (D7 Week 3 and D1 Week 4)
3b(i)	Weeks 4-5	7.5 g	Placebo	
3b(ii)	Weeks 6-8	7.5 g	Placebo	Partial Efficacy Assessment** done at Visit 5 (D1 Week 6) Full Efficacy Assessment* at Visit 6 (D7 Week 8 and D1 Week 9)
3c(i)	Weeks 9-10	9g	Placebo	
3c(ii)	Weeks 11-13	9 g	Placebo	Partial Efficacy Assessment** at Visit 7 (D1 Week 11) Full Efficacy Assessment* at Visit 8 (D7 Week 13 and D1 Week 14)
3c(iii)	Week 14	End of Study Visit (EOS)		
4	Week 15	Follow-up Visit		

1.* Full efficacy assessment occur on the last day of a period and extend into the following day of the next period.

2.** Partial efficacy assessment (MWT and PSG are excluded) occur following the first two weeks on the 7.5 g dose and following the first two weeks on the 9 g dose during respective periods.

3.*** Maximum of 2 day turnaround for PSG and MWT results from Central Scoring Laboratory

Table 2: Study Design

Screening and Baseline		Rand	Dose Titration			Dose Titration			Stable Dosing					EOS	FU		
					7.5g	7.5g	7.5g	7.5g	7.5g	7.5g	9.0g	9.0g	9.0g	9.0g	9.0g		
		Arm 1	4.5g	6g	6g												
		Arm 2	Placebo														
				Placebo	Placebo												
						Placebo	Placebo	Placebo	Placebo	Placebo							
											Placebo	Placebo	Placebo	Placebo	Placebo		
Visit 1	Visit 2*		Visit 3***	Visit 4*		Visit 5**	Visit 6*		Visit 7**		Visit 8*	Visit 9					

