4.7 SAFETY ANALYSES

Safety evaluations will be performed on the safety population using the actual treatment administered.

Adverse events will be identified as treatment-emergent (TEAE) if the event occurs or increases in severity after the first dose of study medication is taken. Adverse events will be identified as mild, moderate or severe and related to the treatment as reported on the CRF. The adverse events will be assigned a preferred term (PT) and a system organ class (SOC) according to the Medical Dictionary for Regulatory Activities (MedDRA), latest version. In counting the number of events reported, a continuous event, i.e., an event reported more than once and which did not cease, will be counted only once with the worst recorded severity. Non-continuous AEs reported multiple times by the same subject will be counted as multiple events. AEs will be assigned to the period of the study corresponding to the time of onset. Events presenting immediately prior to the first dose of study medication that do not worsen in severity, will not be included. In deriving the tabulation relating to preferred term reporting, the severity of a recurrent AE will be taken to be the most severe and the relationship to study medication as the most probable within the relevant period of the study. Total exposure to FT218 will be determined in terms of number of days and dose.

Laboratory data will be summarized in terms of the proportions of patients with clinically notable abnormalities using normal ranges. Shift tables will tabulate baseline to most extreme post baseline values. Summary statistics of raw data and change from baseline values will be obtained including means, medians, standard deviations and ranges will be produced.

The summaries will include subjects in the safety population who have had at least one laboratory test performed after the first study drug administration with an available baseline laboratory value. Baseline values will be measured as the last available measure before taking study drug.

[REDACTED]

[REDACTED]

[REDACTED]

[REDACTED]

[REDACTED]

[REDACTED]

[REDACTED]

[REDACTED]

[REDACTED]

[REDACTED]

[REDACTED]

[REDACTED]

[REDACTED]

[REDACTED]

[REDACTED]

[REDACTED]

[REDACTED]

[REDACTED]

[REDACTED]

[REDACTED]

[REDACTED]

[REDACTED]	[REDACTED]	[REDACTED]
[REDACTED]	[REDACTED]	[REDACTED]
[REDACTED]	[REDACTED]	[REDACTED]
[REDACTED]	[REDACTED]	[REDACTED]
[REDACTED]	[REDACTED]	[REDACTED]
[REDACTED]	[REDACTED]	[REDACTED]

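### The rule for recording worsening of a baseline condition as an AE omits the follow-up period and contradicts the protocol's other AE rules

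*Protocol*

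**What the plan says.** Protocol 10.1.2.1, under documentation and reporting of AEs, has a specific rule for medical-history conditions that are ongoing at the first visit. They "will only be recorded as AEs if during the screening and assessment period or double-blind period there is deterioration". Follow-up is not among the periods named.

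Other text sets different limits, or none:

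- **Protocol 10.1.2.1, the sentence just before.** Attention to AEs runs "starting from signing of the informed consent to the follow-up visit which takes place 1 week after study completion", with a matching one-week window after premature withdrawal.
- **Protocol 10.1.2.1, follow-up of AEs.** Subjects are followed for 7 days after the last dose, and "any AEs that occur during this time should be reported according to the procedures outlined above".
- **Protocol 9.3.1.** At Visit 9, all AEs including residual drug effects are to be reported. AEs that began in the double-blind period are re-evaluated, and "any new AEs should be recorded".
- **Protocol 10.1.2.4.** "Any deterioration in condition will be reported as an AE", with no period attached.
- **SAP 4.7, with a matching definition in Protocol 10.1.2.1.** An AE is treatment-emergent "if the event occurs or increases in severity after the first dose of study medication is taken". No end date is given.

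On the analysis side, Protocol 11.10 ties the safety evaluation to the evaluation period used for efficacy.

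**The concern.** The word "only" makes the baseline-condition rule exclusive, and the double-blind period it names is not the follow-up period. A condition present at Visit 1 that first worsens after that period is, on this sentence, not an AE. The same symptom arising for the first time in a subject without that history is one.

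Visit 9 is a safety visit meant to find residual effects, and the AE definition in 10.1.2.1 includes signs and symptoms of withdrawal. A site that follows the specific sentence would leave out part of what the visit is meant to collect, while a site that follows 10.1.2.4 would record it. The SAP cannot repair the difference later, because it tabulates only what reaches the eCRF. At stake are the completeness and consistency of non-serious AE data after stopping. The efficacy result is not affected.

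**Working it through.** The plan states no figure on this point. The check is a comparison of texts and a day count.

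**Step 1. Is follow-up outside the double-blind period?** Yes. Protocol section 9 counts the visits as "six in Period 3 (the double-blind period) concluding with a single follow-up visit in Period 4". SAP 2.3 lists four separate periods: "screening, wash-out/baseline (which includes randomization), double-blind-treatment and follow-up". Visit 9 therefore lies outside the periods named in the baseline-condition rule.

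**Step 2. Do the other rules resolve it?** They do not.

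- The consent-to-follow-up window and the seven-day rule say when AEs are collected. The baseline-condition sentence says whether this kind of event is an AE at all. A site can read the broad window as including the worsening, or the narrow sentence as excluding it.
- At Visit 9 a site re-evaluates AEs with double-blind onset and records new ones. Under the exclusive sentence, first worsening of a baseline condition in follow-up is neither.
- Protocol 10.1.2.4 conflicts directly, since it makes deterioration an AE without limit of time.
- The treatment-emergent definition also counts an increase in severity at any time after the first dose. It presupposes that such worsening has been recorded.

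Protocol 10.1.2.1 tells investigators to apply the protocol's AE definitions but does not say which rule takes precedence.

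**Step 3. How long is the uncovered window for completers?** Count days from Week 1 Day 1.

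- Last dose, Week 13 Day 7 (SAP 4.1.4): 13 × 7 = day 91.
- Visit 9, Week 15 Day 1, +4/-0 (Protocol 9.3.1): 14 × 7 + 1 = day 99, at the latest 99 + 4 = day 103.
- Week 14: days 92 to 98.

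| Where the double-blind period ends | Uncovered window | Length |
|---|---|---|
| End of Week 14, taken as Period 3c(iii) | Days 99 to 103 | Week 15 Day 1 to at most Day 5 |
| Last dose | Day 91 to day 99–103 | 99 − 91 = 8 to 103 − 91 = 12 days |

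SAP Table 1 gives Week 14 to Period 3c(iii) and Week 15 to Period 4, and the design table in Protocol 8.1.1 shows the same sequence. That supports the first row. Protocol 9.2.6, however, labels Visit 8 itself as Period 3c(iii) and dates it Week 13 Day 7, and SAP 4.1.4 ends treatment that day. That leaves the second row open. The documents do not settle which applies.

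**Step 4. Early leavers.** Protocol 8.3.4 follows them for one week after the last dose. The week-based period map does not say whether that week is still double-blind for them, so up to 7 days are arguably uncovered, at whatever dose they had reached.

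**Step 5. Would recorded follow-up events be analysed?** That is unclear. Protocol 11.10 uses the efficacy evaluation period, and the comparison windows in SAP 4.1.3 end at Week 13. SAP 4.7 assigns each AE to the period of onset. Read together, follow-up-onset AEs may fall outside the comparison between arms even when they are recorded.

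**The case against.** The strongest reply is that this is loose drafting with little practical effect. The sentence evidently exists to keep stable medical history out of the AE log. Much of the remaining text would capture a true worsening: the AE definition lists withdrawal symptoms and has a broad clause on other clinical deterioration, Visit 9 asks for all AEs including residual effects, and the SAE definition in 10.1.2.1.1 has no period limit. On the SAP Table 1 map, the week right after the last dose is still inside Period 3, so for completers the days most relevant to stopping are covered.

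Much of this stands. Serious worsening should still be reported, many sites would probably record non-serious worsening too, and the completers' window may be no more than five calendar days. The reply does not remove the contradiction, because the one rule written for baseline conditions is exclusive and the capturing text is general.

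A reader might go further and infer that such worsening is simply not counted. The documents do not support that: they give conflicting instructions, and inconsistent recording is as likely a result as omission. Nor is the gap specific to stopping 9 g. It applies equally to placebo and to subjects who leave at a lower dose.

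**Conclusion.** The point holds as an internal contradiction in the AE recording rules. Worsening of a baseline condition in Period 4 is excluded by one sentence and included by several others, and the one-week follow-up of early leavers is arguably affected too. The likely result is inconsistent or missing recording of non-serious events.

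For completers the window is Week 15 Day 1 to Day 5 if Week 14 belongs to Period 3c(iii), or 8 to 12 days if the double-blind period ends at the last dose.

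It is tempting to conclude that events are lost mainly from the active arm, so that the AE comparison is biased toward no difference. That does not follow from the documents. The loss in each arm would be the share of subjects with an ongoing condition, times the probability of worsening after stopping, times the probability that the site does not record it. The documents give none of these, and any imbalance would come from the values assumed. The effect on the comparison also depends on Protocol 11.10, which may leave follow-up events out in any case. The size and direction of any effect are therefore not established.

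**What to change.** Amend the sentence in Protocol 10.1.2.1 to say, in substance: a medical-history condition captured at the first visit is recorded as an AE if it deteriorates at any time from informed consent through Visit 9 or, after early withdrawal, through the one-week follow-up. This agrees with the general AE window, 10.1.2.4 and the treatment-emergent definition, and it removes the need to settle where Week 14 belongs for this purpose.

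In the same edit, reconcile Protocol 11.10 with SAP 4.7 so that AEs with onset in follow-up are included in the safety tabulation by arm. Without this, better recording may not reach the analysis.

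The cost is one sentence in 10.1.2.1 and a clarification of the safety evaluation period. Visit 9 already collects AEs, so no procedure is added. AE counts may rise slightly.

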10.1.2.1.1 Serious Adverse Events

Serious Adverse Event Definition

An SAE is any untoward medical occurrence or effect that, at any dose,

- Results in death
- Is life-threatening (an AE is life-threatening if the subject was at immediate risk of death from the event as it occurred, i.e. it does not include a reaction that might have caused death if it had occurred in a more serious form)
- Requires or prolongs inpatient hospitalization. (Complications occurring during hospitalization are AEs and are SAEs if they cause prolongation of the current hospitalization. Hospitalization for elective treatment of a preexisting nonworsening condition is not, however, considered an AE. The details of such hospitalizations must be recorded on the medical history or physical examination page of the eCRF)
- Results in persistent or significant disability/incapacity. (An AE is incapacitating or disabling if it results in a substantial and/or permanent disruption of the subject’s ability to carry out normal life functions)
- Results in a congenital anomaly/birth defect

In addition, medical and scientific judgement is required to decide if prompt notification is required in situations other than those defined for SAEs above. This may include any event that the investigator regards as serious that did not strictly meet the criteria above but may have jeopardized the subject or required intervention to prevent one of the outcomes listed above, or that would suggest any significant hazard, contraindication, side effect, or precaution that may be associated with the use of the investigational product.

Reporting of Serious Adverse Events

If a SAE occurs, the CRO/sponsor is to be notified within 24 hours of awareness of the event by the investigator. If the SAE is fatal or life-threatening, notification to the CRO/sponsor must be made immediately, irrespective of the extent of available AE information. This timeframe also

applies to additional new information (follow-up) on previously forwarded SAE reports as well as to the initial and follow-up reporting of exposure in utero cases.

In the rare event that the investigator does not become aware of the occurrence of a SAE immediately (eg, if an outpatient study subject initially seeks treatment elsewhere) the investigator is to report the event within 24 hours after learning of it and document the time of his/her first awareness of the AE.

For all SAEs, the investigator is obligated to pursue and provide information to the CRO/sponsor in accordance with the timeframes for reporting specified above. In addition, an investigator may be requested by the CRO/sponsor to obtain specific additional follow-up information in an expedited fashion. This information may be more detailed than that captured on the SAE form. It will describe the SAE in enough detail to allow for a complete medical assessment of the case. Additional information concomitant medications and illnesses must be provided. In the case of a subject death, a summary of available autopsy findings must be submitted as soon as possible to the CRO/sponsor.

The SAE forms must be faxed **within 24 hours** for the attention of

INC Research Drug Safety
[contact]
e-mail: [contact]

The immediate SAE report will be made by the investigator within a very short period of time and under no circumstances should this exceed 24 hours following knowledge of the SAE.

Although the information required for completion of a SAE report form may not be available within the specified time period, an initial report should be submitted with the following information available.

- Subject ID (screening/randomization number)
- The suspect product/formulation – as blinded only the dose strength will be detailed
- An event or outcome that can be identified as serious
- The seriousness criterion
- The causal assessment (note: this may change as more information is learned, however, an assessment **MUST** accompany the original report)

All SAE information must be recorded on an SAE form and sent within 24 hours or 1 business day of learning of the report to INC Drug Safety. Additional information received for a case (follow-up or corrections to the original case) need to be detailed on an SAE form and sent to INC Drug Safety. The SAE will be followed up until a final outcome and date are available. Instances of death, congenital abnormality, or an event that is of such clinical concern as to influence the overall assessment of safety, if brought to the attention of the investigator at any time after cessation of study drug administration and linked by the investigator to this study, should be reported to the study monitor.

The sponsor/CRO will promptly notify all relevant investigators and the regulatory authorities of findings that could adversely affect the safety of subjects, impact on the conduct of the study or alter the IEC/IRB approval/favorable opinion of the study. In addition, CRO/sponsor will expedite the reporting to all concerned investigators, to the IECs/IRBs, where required, and to the regulatory authorities of all adverse reactions that are both serious and unexpected.

Details of the procedures to be followed if a pregnancy occurs are provided in [Section 8.3.4](#).

Although pregnancy is not an SAE, and an elective abortion is not an SAE, any spontaneous abortion and/or any pregnancy that meets any regulatory serious criterion, or any pregnancy with an outcome for the pregnant person or the infant that meets regulatory serious criterion will be captured as an SAE.

